c) *Preliminary data - Switching menthol smokers to non-menthol cigarettes:* In an open-label study, 31 African American menthol cigarettes smokers (smoking ≥ 8 cigarettes per day) completed a study in which they were asked to abstain from smoking menthol cigarettes for a 4 week period. Subjects were seen at a screening visit, a baseline visit and 1 week, 2 weeks and 4 weeks after stopping smoking menthol cigarettes. Subjects were given no specific instructions regarding how to cope with the inability to smoke menthol cigarettes (as would be the case if a menthol ban were enacted). All subjects reported switching to non-menthol cigarettes with three subjects making a smoking cessation attempt during the 4 week period. At the conclusion of the study, subjects were asked to rate on a 10 point scale how difficult it was to quit menthol cigarettes (1=easy; 10=hard) and the extent to which they were supportive of banning menthol cigarettes (1=not supportive; 10= very supportive). Subjects indicated that quitting menthol cigarettes was difficult (average score = 7.2); nonetheless motivation to quit increased slightly during the period (5.3 at baseline vs. 6.3 at week 4, $p=0.03$). Based on a preliminary analysis, upon switching to non-menthol cigarettes, participants smoked slightly fewer cigarettes over the 4 week period (12.0 cigarettes per day during the week prior to baseline vs. 10.6 during week 4, $p=0.14$) and had lower exhaled carbon monoxide concentrations relative to baseline (16.0 ppm at baseline vs. 13.2 ppm at week 4, $p=0.05$). At the conclusion of the study, subjects were generally supportive of banning menthol (average score = 7.1). These data suggest that a simulated ban on menthol likely did not result in any greater harm than continued menthol cigarette smoking (i.e. smoking did not increase and motivation to quit was not reduced). Furthermore, after experiencing a simulated menthol ban, menthol smokers were supportive of banning menthol cigarettes. The pilot study did not assess if there was in fact benefit, as would be the case if switching to non-menthol cigarettes resulted in increased subsequent smoking cessation rates. Such an outcome would be consistent with research studies finding that cessation rates are generally higher for African American non-menthol smokers relative to African American menthol smokers.

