Innovation: Although much research has been conducted on the epidemiology and health effects of menthol cigarettes and studies have compared cessation rates among those who prefer menthol vs. non-menthol cigarettes, there is currently little information regarding how smokers of menthol cigarettes would adjust their tobacco use if their preferred cigarettes were no longer available. It seems likely that studies comparing quit rates in those who naturally prefer menthol vs. naturally prefer non-menthol cigarettes may underestimate the beneficial effect of menthol smokers first switching to non-menthol cigarettes prior to a cessation attempt since they would be switching to a non-preferred product and therefore perhaps more likely to quit tobacco use completely. Obtaining data determining if this is indeed the case is critical considering that over 25% of all smokers and over 80% of African American smokers are currently using menthol cigarettes. Our proposed study in which African American menthol cigarettes smokers will switch to non-menthol cigarettes prior to a cessation attempt is innovative in that it attempts to approximate what is likely to happen to smoking cessation success rates were the FDA to ban menthol cigarettes.

Specific Aims/Study Objectives:

In follow-up to our previous study demonstrating that when African American menthol smokers were asked to abstain from menthol cigarettes, they switched to non-menthol cigarettes, were generally supportive of a ban on menthol and experienced an increase in motivation to quit smoking, we are proposing a follow up study to determine if switching to non-menthol cigarettes is an effective first step to cessation. We propose to study the following specific aim:

Determine the impact of a ban on menthol cigarettes on smoking cessation success rates in African American menthol smokers

We hypothesize that a) switching to non-menthol cigarettes before a quit attempt will improve cessation success. We further hypothesize that switching to non-menthol cigarettes prior to cessation will b) increase motivation and self-efficacy to quit and c) enhance support for a ban on menthol cigarettes. We anticipate that no greater harm will result from the elimination of menthol cigarettes.

Research Design and Methods:

Sampling Plan

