Design Overview: This study will randomize 140 African American menthol cigarette smokers to receive either menthol cigarettes (i.e. continue smoking menthol cigarettes) or non-menthol cigarettes for a four week period. At the conclusion of the four week period, participants will attempt to quit smoking all cigarettes and will return for follow-up over a 6 month period. Tobacco use, nicotine use, motivation and self-efficacy to quit, nicotine craving and withdrawal measures and support for a ban on menthol cigarettes will be assessed during the study period. Urine cotinine concentrations will be measured at each visit. The primary outcome in this study is time from cessation to the first smoking lapse.

Subjects: In order to be eligible for this study, subjects must: 1) be African American (based on self-identification); 2) smoke primarily menthol cigarettes (greater than 80% of cigarettes smoked are menthol); 3) be between the ages of 18 and 64; 4) Smoke on average, at least 8 cigarettes per day for a period longer than 1 year and 5) express an interest in quitting smoking (rate themselves ≥ 7 on a 10 point scale assessing motivation to quit smoking). Subjects will be excluded if they have: 1) A current unstable medical / psychiatric condition as determined by self-report; 2) Substance abuse within six months of beginning the study based on self-report; 3) Regularly use any form of nicotine or tobacco other than cigarettes or 4) Are pregnant or breast feeding based on self-report (subjects will

be given a urine pregnancy test at the screening visit with pregnancy later in the study and breast feeding based on self-report).

As the risks associated with the study procedures are small, all medical assessments are based on self-report (except for a urine pregnancy test at screening).

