Time to lapse: The primary outcome, time to lapse following the week 0 visit, will be evaluated using a two-sided log-rank test. Since drop-outs could be more likely to lapse, we will perform two tests: one censoring drop-outs at the time of their last visit, and one considering drop-outs as lapsed at the time of their last visit. Randomization of 140 subjects should balance the groups with respect to potential confounding factors, and therefore no adjustment for other factors is planned. The same procedure will be used for the secondary outcome of time to relapse.

Other outcomes: Several continuous outcomes will be measured at baseline and subsequent time points, such as motivation and self-efficacy to quit, support for a menthol ban, severity of craving, perceived health risk, urinary cotinine concentrations, and exhaled CO. We will first calculate the change in each subject's outcome from baseline to the week 26 visit, and compare the study groups using two-sided, two sample t-tests. This will provide a straightforward comparison of whether cessation of menthol use affects long-term nicotine use and perceptions. Second, we will use analysis of variance (ANOVA) with repeated measurements to further analyze trends over all visits in the study period, with group, time, and interaction effects. This would identify more precisely when particular changes took place, or if any group differences emerged around the quit attempt but diminished by the end of the study. Changes in tobacco product use within groups will be summarized qualitatively and by descriptive statistics such as proportions.

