Power and Sample Size: Our primary outcome is time to lapse. Previous studies have found that during a cessation attempt most participants lapse within one week, at a median of 2-3 days after their quit attempt (35, 36). We plan on enrolling 140 subjects randomized 1:1 with an approximately 15% post-randomization visit dropout rate, leaving 120 subjects with data on time to lapse. This gives us over 80% power to detect a 1.7-fold difference using a significance cutoff of 0.05. We believe that such a difference would be a meaningful indicator of smoking success. The 1.7 fold difference in time to lapse is substantially smaller than is typically seen with medication studies. For example, an analysis by Shiffman et al (J Consult Clin Psychol 2006;74:276-85) found that the median duration of abstinence (i.e. time to lapse) was 6 days for active nicotine patch and 2 days for placebo. That would correspond to a 3 fold difference. Directly comparable data for other interventions is not available, however in a study comparing placebo to five different pharmacotherapy options (i.e. bupropion, nicotine lozenge, patch, bupropion + lozenge, patch + lozenge), the time until 50% of participants in the placebo group lapsed was approximately 6 days whereas the time for all other groups (except for nicotine lozenge) the time until 50% of participants lapsed was over 20 days (Japuntich et al. J Consult Clin Psychol 2011;79:34-42), an over 3-fold difference. Likewise, we

would have 80% power to detect an effect size of 0.6 in continuous secondary outcomes (i.e. a difference in group means of 0.6 times the outcome's standard deviation). Since it is not clear what the smallest difference is that would be important to detect, we believe that this sample size will be able to detect a meaningful difference.

Data and Record Keeping:

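### Motivation is a secondary outcome expected to rise, yet entry requires at least 7 of 10: if the same rating is used, a pre-quit rise may be compressed, and the planned unadjusted change-score t-test makes no use of the baseline score as a covariate

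*Combined protocol and SAP*

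**What the plan says.** Inclusion criterion 5 (Research Design and Methods, Subjects) requires that subjects "rate themselves ≥ 7 on a 10 point scale assessing motivation to quit smoking". The protocol explains why: few pilot smokers tried to quit on their own, and this trial studies a quit attempt.

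The Specific Aims state that switching before cessation "will b) increase motivation and self-efficacy to quit". The supporting evidence is the single-arm pilot of 31 subjects (Preliminary data), where "motivation to quit increased slightly during the period (5.3 at baseline vs. 6.3 at week 4", p=0.03). The Background notes that the pilot did not recruit people for their interest in quitting.

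Motivation is scored at the baseline visit and again at later visits (Baseline and Pre-Quit Visits). Under Data Analysis, Other outcomes, the plan is first to "calculate the change in each subject's outcome from baseline to the week 26 visit" and "compare the study groups using two-sided, two sample t-tests", then to use "analysis of variance (ANOVA) with repeated measurements to further analyze trends over all visits in the study period". The Power and Sample Size section gives one figure for all continuous secondary outcomes: 80% power at 0.6 of the outcome's standard deviation.

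The plan does not name the motivation outcome instrument. It gives no SD or distribution for it and does not mention an upper bound.

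**The concern.** The trial looks for a rise in people selected for already scoring high. On the entry scale, someone at 7 can rise by 3 points and someone at 10 cannot rise at all. A raw change score records the latter as zero whatever happened to their motivation. The pilot rise began from a mean of 5.3, below the new entry floor if the pilot used a comparable scale.

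At stake is how half of hypothesis (b) is read. A null result on motivation could be reported as no effect of switching when part of it is lack of room on the scale. The analysis section has no step that would show this.

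**Working it through.** **The plan's own figure.** Normal approximation, two-sided 0.05, 60 per arm (120 subjects, the number the plan gives for time to lapse), effect 0.6 SD:

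Power = Φ(0.6 × √(60/2) − 1.96) = Φ(3.286 − 1.96) = Φ(1.326) = 90.8%.

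The stated 80% corresponds to 44 per arm: Φ(0.6 × √22 − 1.96) = Φ(0.854) = 80.4%. The gap is conservative and separate from the ceiling question.

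**Direct arithmetic on the ceiling.** On a whole-point scale, a true 1-point rise is realised by everyone except those already at 10, so realised rise = 1 − (share at 10). For entrants with shares at 7/8/9/10 of:
- 40/30/20/10%: 0.90
- 25/25/25/25%: 0.75
- 10/20/20/50%: 0.50

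**Simulation.** The documents give no distribution, so these inputs are assumptions:
- latent motivation normal, mean 5.3, 7, 8.5 or 9.5, SD 2.5, reliability 0.7
- screening, baseline and follow-up scores rounded and bounded to 1–10
- entry if the screening score is 7 or more
- 60 per arm, true between-arm effect of 1 point

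Regression to the mean between screening and baseline, and the smaller SD caused by the bound, are both included.

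Unbounded benchmark: SD of change = √(2 × (1 − 0.7) × 2.5²) = 1.94; standard error = 1.94 × √(2/60) = 0.354; power = Φ(1/0.354 − 1.96) = Φ(0.87), about 81%. Simulated values are about 80%.

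| Latent mean | Share at 10, baseline | Observed difference, no drift | t-test power, no drift | Baseline-adjusted (ANCOVA) power, no drift | Observed difference, both arms fall 2 points | t-test power, both arms fall 2 points |
|---|---|---|---|---|---|---|
| 5.3 | about 13% | 0.87 | 74% | 87% | 0.96 | 81% |
| 7 | about 26% | 0.75 | 68% | 83% | 0.94 | 79% |
| 8.5 | about 42% | 0.58 | 57% | 74% | 0.85 | 79% |
| 9.5 | about 56% | 0.43 | 45% | 65% | 0.75 | 74% |

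The no-drift differences track 1 − (share at 10): 0.87, 0.74, 0.58, 0.44. The change-score SD also shrinks, from about 1.87 in the first row to 1.29 in the last, which offsets part of the loss. Last row by hand: Φ((0.43/1.29) × √30 − 1.96) = Φ(−0.13), about 45%.

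**Where each column applies.** No drift is the nearer description of week 0, the end of the four-week switching period. The planned t-test is at week 26, after the quit attempt. The 2-point fall is an assumption; the documents give no drift.

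**What the covariate does.** ANCOVA as simulated has no ceiling handling. It gains 13, 15, 17 and 20 power points (87−74, 83−68, 74−57, 65−45) by using the baseline score efficiently. It does not undo the compression of the estimate.

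**The case against.** **The large losses rest on assumptions.** No SD, distribution or share at 10 is in the documents, and neither the outcome instrument nor the pilot's motivation scale is identified. This stands. With the only documented mean, 5.3, the simulated loss is about 6 points (80% to 74%). Simulations at that mean with SD 2.0–2.5 and correlation 0.4–0.8 put the cost of the entry floor at 0–3 points. Larger losses need a more motivated pool. That is plausible because the trial recruits people who want to quit, but it is not documented.

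**The planned contrast is at week 26.** A group difference in change can also arise from a smaller fall in the switched arm, and a ceiling hardly binds once scores have dropped. This stands too. However, hypothesis (b) concerns switching before cessation, the pilot rise was measured over four weeks, and the repeated-measures analysis covers the pre-quit visits, where the ceiling binds most.

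**Stronger readings that the documents do not support.** A reader might infer that the 0.6 SD power figure fails for motivation. It does not: that figure is in units of the observed outcome's SD. A ceiling changes how many underlying points 0.6 SD represents, not the power at 0.6 observed SD. A reader might also infer that the t-test is biased. It is, if the target is an underlying unbounded motivation; it is not biased by the ceiling for the mean rating difference in this deliberately motivated population. Finally, a censored model might seem the natural main analysis, because it returned 0.96–0.99 of the true 1 point in simulation. That is circular, since the data were generated as a clipped normal. Its power (88%, 81%, 76%, 67%) is nearly matched by plain ANCOVA.

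**Conclusion.** The point holds in conditional form. The tension between the entry floor and the predicted rise is in the text, and the plan does not address it. If the outcome is the 10-point entry rating, a pre-quit rise may be compressed: a true 1-point effect would appear as roughly 0.87 to 0.43 points, with change-score t-test power of about 74% to 45%, as the baseline share at 10 goes from 13% to 56%. By week 26 the loss is small in most scenarios if motivation has fallen. The documents do not show that the planned estimate or its power will in fact shrink.

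The scope is motivation alone. The entry rule sets no floor on self-efficacy or ban support, and time to lapse is untouched. What holds whether or not a ceiling binds is that a baseline score is collected but not used as a covariate in the planned t-test.

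**What to change.** Keep the entry rule. In Data Analysis, Other outcomes:

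- Name the motivation instrument and its range.
- For motivation, replace the unadjusted change-score t-test with a group comparison adjusted for the baseline-visit score (ANCOVA). The result is still a mean difference in rating points.
- Include the week 0 contrast, which the repeated-measures analysis already covers, alongside week 26.
- Report the share of subjects at the maximum by arm and visit.
- Add a model treating the maximum as censored, or a proportional-odds model, as a sensitivity analysis only. If many subjects are at 10, do not report a null on motivation as no effect.

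The 0.6 SD power statement needs no withdrawal on this account.

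The cost is SAP wording and standard models on data already being collected, with no new visits or subjects. The sensitivity model carries a distributional or proportional-odds assumption and is harder to read than a difference in points, which is why it should not lead.

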At all visits, subjects will be asked to provide a urine sample. The urine will be used to measure cotinine concentrations and may in the future also be used to measure other markers related to smoking menthol cigarettes (such as other nicotine metabolites, menthol concentrations, tobacco toxicants, etc.). Subjects will also be asked to bring in their smoking diary in which they are to record cigarettes smoked as well as any other tobacco or nicotine products used (including e-cigarettes).

Follow up visits: Starting at Week 0 (quit date); subjects will attend follow up visits at weeks 1, 2, 4, 6, 8, 12 and 26. At each of these visits subjects will be asked if they have smoked at all since their previous visit. Exhaled carbon monoxide (CO) will be measured with an exhaled CO less than 8 ppm and a urine cotinine concentration of less than 50 ng/ml confirming abstinence (16). Smoking diaries will be used to determine time to lapse (time from their quit attempt until any smoking occurs) and time to relapse (time from their quit attempt until the first day of seven consecutive days that a cigarette is smoked).

Subjects will be paid \$20 for the screening visit, \$30 for each of the 7 visits between week 0 and week 12 with a \$100 bonus if they complete all visits up to week 12 and have complied with study related procedures. We anticipate that it will be more difficult to retain subjects through the 6 month visit; therefore subjects will receive \$60 for that visit. Since it is imperative that subjects honestly report any smoking during the study (in order to calculate time to lapse), payment during the cessation phase will not be contingent on successful abstinence. Subjects that relapse and resume smoking during the study will still be eligible to continue in the study. However, subjects that fail to follow study procedures (e.g. provide urine samples, fill out questionnaires, etc.) will be removed from the study.

Data and Safety Monitoring Plan:

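### Removing subjects who miss urine samples or questionnaires causes avoidable loss of lapse data, which the two planned log-rank tests do not reliably bracket

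*Combined protocol and SAP*

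**What the plan says.** Implementation Plan, Follow up visits, contains the rule: "subjects that fail to follow study procedures (e.g. provide urine samples, fill out questionnaires, etc.) will be removed from the study". The same section states that "Subjects that relapse and resume smoking during the study will still be eligible to continue in the study" and that "payment during the cessation phase will not be contingent on successful abstinence". A $100 bonus goes to subjects who "complete all visits up to week 12 and have complied with study related procedures". On the endpoint, "Smoking diaries will be used to determine time to lapse", with exhaled CO and urine cotinine confirming abstinence; after the quit date "subjects will attend follow up visits at weeks 1, 2, 4, 6, 8, 12 and 26".

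Data Analysis, Time to lapse, has the primary outcome "evaluated using a two-sided log-rank test". It gives a reason for running that test twice: "Since drop-outs could be more likely to lapse". One run censors drop-outs at their last visit and the other counts them as lapsed there.

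The plan does not say whether a removed subject is a drop-out, which visit is the last one for someone removed at a visit, how many missed procedures trigger removal, or which test decides if the two disagree.

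**The concern.** Removal ends participation, not just payment. A subject who attends but gives no urine sample could still be asked when smoking resumed, yet under the rule that question need never be put. The rest of the section is built to protect ascertainment of lapse: relapsers stay in, and payment does not depend on abstinence. The removal rule works against that aim.

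Two things are at stake. Lapse times are lost through the plan's own action and not through unavoidable attrition. If the loss is related to lapse and differs between arms, the primary comparison is distorted, and the size and even the pattern of the distortion depend on a term the plan leaves undefined.

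**Working it through.** **Inputs from the plan (Power and Sample Size; Follow up visits).** 140 subjects randomised 1:1, about 15% dropout, 120 with data; median time to lapse 2–3 days (2.5 used here); visits at weeks 1, 2, 4, 6, 8, 12 and 26; two-sided 0.05; target 1.7-fold difference.

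**The plan's own power figure.** Schoenfeld: power = Φ(√(events/4) × ln 1.7 − 1.96).
- 120 events: √30 × 0.5306 − 1.96 = 0.946, power 82.8%. The stated figure of over 80% is reproduced.
- 140 events (everyone followed to lapse): √35 × 0.5306 − 1.96 = 1.179, power about 88%.

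**Lapse times lost under equal 10% removal of first-week lapsers.**
- Constant hazard: proportion lapsing by day 7 = 1 − 0.5^(7/2.5) = 0.86; 0.10 × 0.86 × 140 = 12.
- Weibull, shape 0.5: 1 − exp(−ln 2 × √(7/2.5)) = 0.69; 0.10 × 0.69 × 140 = 9.7, about 10.

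**Effect on the two tests.** Simulation of 70 per arm with no true effect, constant hazard, median 2.5 days and 1,000 trials per scenario. The Monte Carlo standard error at 5% is √(0.05 × 0.95/1000) = 0.7 points. A stated share of lapsers in each arm is removed with the lapse unrecorded. All removal shares are assumptions, set so that about 15% of subjects are removed overall. HR is the approximate hazard ratio, menthol over non-menthol; above 1 favours non-menthol.

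| Removed, menthol / non-menthol | Last visit means | Censored: HR, type I error | Counted as lapsed: HR, type I error |
|---|---|---|---|
| 15% / 15% | visit before failure | 1.00, 5.6% | 1.00, 4.7% |
| 15% / 15% | visit of refusal | 1.01, 5.6% | 1.01, 5.6% |
| 10% / 20% | visit before failure | 1.04, 5.9% | 0.93, 6.9% |
| 10% / 20% | visit of refusal | 1.24, 21.3% | 1.15, 12.5% |
| 5% / 25% | visit before failure | 1.08, 7.1% | 0.86, 13.7% |
| 5% / 25% | visit of refusal | 1.56, 64.0% | 1.34, 34.6% |

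Swapping the shares between arms reverses the direction in every unequal row.

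The reason is simple. With a median of 2.5 days, the visit before the failure is usually week 0. Censoring there drops lapsers and flatters the arm that loses more of them; scoring a lapse there dates it too early and penalises that arm. If the last visit is the week 1 visit itself, a subject who lapsed around day 2 or 3 is carried lapse-free to day 7 in both tests, so both flatter the same arm.

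**A heavier case.** With 10% against 30% of first-week lapsers removed, under constant or Weibull hazard, type I error is 5–11% across both tests on the first reading. On the second it is 26–48% (censored) and 11–30% (counted as lapsed). The directions are as in the table.

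**Power with a true 1.7-fold effect and equal 15% removal.** Full data give about 87%. Censored and counted-as-lapsed give 86% and 84% on the first reading, and 64% and 80% on the second.

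**The case against.** The case against has real force.

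- **The link to lapse is inferred.** No part of the protocol ties missed samples or questionnaires to lapsing. Admitting a lapse costs the subject nothing, whereas refusing a sample costs participation. A reader might infer that the rule turns lapsers into drop-outs; the document says only that drop-outs in general could be more likely to lapse. This stands.
- **Unequal removal is not documented.** A reader might infer that the switched arm will comply less because it smokes a non-preferred product. That period ends at week 0, when the lapse clock starts, and both arms then follow the same procedures. Which arm would lose more, if either, is unknown. This stands.
- **Exposure is limited.** Most lapses are expected in the first week. A lapse already in the diary or reported at week 1 is not undone by later removal, and nothing says collected data are discarded. This stands, although nothing says explicitly that such dates are kept.
- **The heavier case is a stress test.** 0.86 × 70 × (0.10 + 0.30) = 24 removals, or 0.69 × 70 × 0.40 = 19: 17% or 14% of 140, against about 15% dropout from all causes. This stands.
- **Two tests are already planned for lapse-related drop-out.** This stands only in part. A reader might infer that they always err in opposite directions and so enclose the truth. That needs both unequal removal and the last visit read as the one before the failure, and the plan specifies neither.
- **The bonus stops at week 12, and telephone reports lack CO or cotinine confirmation.** Both are true. Week 26 has its own $60 payment that could be withheld, and an unconfirmed lapse date is more informative than none.

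**Conclusion.** The point holds in a limited form. Followed as written, the rule creates avoidable missing data on the primary endpoint, and the two planned tests do not cure it. It does not follow that the trial is biased. With equal removal and no true effect neither test is biased, and the cost is about 10 to 12 lapse times at 10% removal. With unequal removal of unrecorded lapsers the bias ranges from slight (type I error 6–7% at 10%/20%, visit-before-failure reading) to severe (64% and 35% at 5%/25%, visit-of-refusal reading). In the severe case both tests would agree on the same false result.

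These sizes rest on assumed removal rates, an assumed link between lapse and missed procedures, and a 2.5-day median. The missing follow-up after removal and the undefined last visit do not depend on those assumptions. This is a cheap improvement, not a fatal flaw.

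**What to change.** In Implementation Plan, Follow up visits, replace removal with the following:

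- A subject who does not complete a procedure forfeits the related visit payment or the compliance bonus but stays in outcome follow-up.
- All lapse dates already recorded are kept.
- Missing lapse dates are obtained by interview or telephone at the next contact.
- The subject is analysed as randomised.

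In Data Analysis, Time to lapse, define the last visit for any remaining drop-outs, and report procedure non-compliance by arm. Leave the investigator's discontinuation review under Data and Safety Monitoring Plan unchanged.

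The cost is a protocol wording change and a few extra contacts by existing staff. The downside is small: some outcomes will be self-reported without CO or cotinine confirmation.
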